7.3.2 LIGHT TREATMENT PROCEDURE

Seventeen (17) to 24 days after surgery in the primary eye, the subject will return for the Postop Week 3 LAL evaluation and a 1st adjustment treatment of the LAL. Subsequent second and third adjustment treatments, if necessary, will all be separated by 3-7 days. A second adjustment treatment will be performed if guided by the LDD.

[figure not shown]
1st lock-in treatment 3-7 days after the final adjustment treatment. If necessary, lock-in #2 may be performed 3-7 days after lock-in #1. Depending on the adjustment(s) performed, subjects will receive one to three adjustments and one or two lock-in treatments.

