Fundus Exam	X				X							X	X	
Fundus Photos	X				X							X	X	
					X	X^1	X^1	X^1	X^1	X^1	X^1	X ¹	X ¹	
Adverse Events		X	X	X	X	X	X	X	X	X	X	X	X	X

Table 3. Schedule of Visits and Clinical Parameters for Fellow Study Eyes (Control)

able 3. Schedule of Visits and Clinica	ar r ar	amett		1, 6110	w Stu	uy Ly	(C)	1111111
Visits	Preop OU	Operative Control	Postop Day 1 Control	Postop Week 1 Control	Postop Week 3 Control	Postop Month 3 Control	Postop Month 6 Control	Unscheduled Visit ¹
Demographics	X							
	X				X	X	X	
					X	X	X	
Ocular History Including Medications	X	X	X	X	X	X	X	
Ocular Biometry (ACD + Axial length)	X							
Subjective Symptoms/Complaints (Subject reported)			X	X	X	X	X	X
Corneal Topography	X				M			
Autorefraction				X	M	M	M	
Corneal Keratometry	X				M		M	
Specular Microscopy	X				M		M	
Uncorrected distance visual acuity (UCDVA)	X		X	X	M	M	M	X
Manifest Refraction	X			X	M	M	M	X
Best corrected Visual Acuity Distance (BCDVA)	X			X	M	M	M	X
					M	M	M	
					M	M	M	
Distance Corrected Contrast Sensitivity (Mesopic/Photopic w and w/o glare)					M		M	
Intraocular Pressure	X		X	X	X	X	X	
Slit Lamp Exam	X		X	X	X	X	X	X

Visits	Preop OU	Operative Control	Postop Day 1 Control	Postop Week 1 Control	Postop Week 3 Control	Postop Month 3 Control	Postop Month 6 Control	Unscheduled Visit ¹
Dilated Pupil Diameter	X				X			
Fundus Exam	X				X		X	
Fundus Photos	X				X		X	
Spectral Domain Optical Coherence Tomography (SD-OCT)					X			
Adverse Events		X	X	X	X	X	X	X

¹Tests indicated with an "X" must be performed at each unscheduled visit. Other tests may be conducted based on the investigator's assessment of the subject.

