8.2 GENERAL CONSIDERATION

The statistical analysis of the data will be performed using SAS version 9.3 or higher or another industry standard statistical software package. Continuous variables will be summarized using descriptive statistics, specifically the mean, median, standard deviation, minimum and maximum. Categorical variables will be summarized by frequencies and percentages. The summaries will be provided for the LAL eyes and Control eyes separately. For continuous outcomes, the difference between the two eyes of the same subject will be calculated and summarized by using descriptive statistics for continuous outcomes.

Unless otherwise specified, all p-values will be two-sided for a two-sided significance level of 0.05 (or one-sided for a one-sided significance level of 0.025) and all confidence intervals will be two-sided at 95% confidence level. Safety analyses will be performed on eyes in which IOL implants are attempted.

A detailed statistical analysis plan (SAP) will be developed and finalized prior to the locking of the database for this study.

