For the contrast sensitivity (in log units) at each spatial frequency level under each of the four test conditions (photopic with and without glare and mesopic with and without glare) at Postop Week 3 and Postop Month 6 will be summarized by mean, standard deviation, median, minimum and maximum for the eyes participated in the contrast sensitivity substudy. The number and percent of eyes that cannot see any plate will be presented.

The mean of "within-eye" loss of contrast sensitivity from Postop Week 3 to Postop Month 6 will be provided with the 1-sided 95% confidence interval for each spatial frequency. The percentage of eyes showing > 0.3 log unit loss at two or more spatial frequencies will be calculated.

Increased Astigmatism

Number and percent of eyes with increased astigmatism from Postop Week 3 will be reported at each postoperative visit

Subjective Symptoms and Complaints

Number and percent of eyes will be summarized for each reported subjective symptom.

Other Ocular Examinations

Slit lamp and fundus exam findings and IOP including changes will be summarized descriptively. Number of subjects with fundus exam changes from the pre-op and Postop Week 3 evaluation will be summarized.

Endothelial Cell Density (ECD) and Morphology Data

Specular Microscopy data includes endothelial cell density, hexagonality and coefficient of variation. These endpoints will be summarized by mean, standard deviation, 95% CI of the mean, minimum and maximum. The change in ECD and percent change in ECD from preoperative will be summarized in the same manner. Additionally, ECD change and ECD percent change for each eye will be calculated between Preoperative and Postop Week 3 and between Postop Week 3 and Postop Month 6. These changes will be summarized by mean, standard deviation, 95% CI for mean, minimum, and maximum. Additionally, at Postop Week 3 and Postop Month 6, the number and percent of eyes with an ECD of < 1500 cells/mm² and number and percent of eyes with an ECD change from baseline \leq -25% (i.e. and an ECD loss of \geq 25%) along with the 95% confidence interval of the percentage derived per binomial distribution will be calculated for the LAL eyes and Control eyes separately.

The percent ECD loss (%ECL) at Postop Month 6 for each eye and the difference between %ECL (Δ %ECL) at Postop Month 6 for each subject are derived as follows:

%ECL = (ECD at Preop – ECD at Postop Month 6)
$$\div$$

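### Contrast sensitivity gets an interval only for within-eye loss from Week 3; a paired LAL-minus-Control limit, as used for endothelial cell loss, should be added

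*Combined protocol and SAP*

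**What the plan says.** Section 8.6 (Distance Corrected Contrast Sensitivity) summarizes log contrast sensitivity at Postop Week 3 and Month 6, by spatial frequency and test condition, "for the eyes participated in the contrast sensitivity substudy". Its one interval is for the within-eye mean: "loss of contrast sensitivity from Postop Week 3 to Postop Month 6 will be provided with the 1-sided 95% confidence interval for each spatial frequency". A second loss measure has no interval: "The percentage of eyes showing > 0.3 log unit loss at two or more spatial frequencies will be calculated".

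Section 8.2 adds two general rules. First, "The summaries will be provided for the LAL eyes and Control eyes separately". Second, "For continuous outcomes, the difference between the two eyes of the same subject will be calculated and summarized by using descriptive statistics". It defines descriptive statistics as "specifically the mean, median, standard deviation, minimum and maximum", so they include no confidence limit. It does not say whether the between-eye difference applies to the visit values, to the change, or to both.

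Week 3 is the baseline before light treatment. On days 17 to 24 after surgery "the subject will return for the Postop Week 3 LAL evaluation and a 1st adjustment treatment of the LAL" (section 7.3.2), and section 7.3.2.3 has required measurements completed before treatment. Tables 2 and 3 in section 7.6 each list "Distance Corrected Contrast Sensitivity (Mesopic/Photopic w and w/o glare" among the masked assessments at Week 3 and Month 6, so both eyes are scheduled for the test at both visits.

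Section 3 gives the Control eyes a role in comparing safety as well as effectiveness. For endothelial cell loss, section 8.6 carries this through: it plans a one-sided 95% upper limit, t-based, for the mean paired LAL-minus-Control difference in percent loss.

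**The concern.** From Week 3 to Month 6 a LAL eye has its light treatments and also goes through whatever any operated eye goes through in those months, such as corneal recovery. The planned interval is centred on the sum of the two. If operated eyes generally improve, a real LAL loss is offset. If they generally worsen, LAL eyes show a loss that the light treatment did not cause.

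The design already contains the remedy. Eyes are randomized within subject, and the Control eye is tested at the matching postoperative visits. The paired contrast separates the treatment effect from shared change, yet the plan gives it no measure of precision. At stake is how well a supportive safety summary answers the comparison with Control that the protocol sets itself.

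**Working it through.** **1. What each quantity estimates.** Let A be any lens-related loss already present at Week 3, L the further loss due to light treatment, and S the loss common to operated eyes between Week 3 and Month 6 (negative if they improve).

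- LAL within-eye loss: L + S
- Control within-eye loss: S
- Paired difference in change: (L + S) − S = L
- Paired Month 6 difference: A + L, because subject-level factors cancel on average under within-subject randomization

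The planned interval targets L + S. Neither it nor the paired difference in change can show A; the paired Month 6 difference can.

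**2. The plan's own paired method.** No figure for contrast sensitivity is stated, so there is none to reproduce. The nearest is the endothelial cell loss power table: SD 4%, margin 5%, 100 pairs, one-sided 0.05. The standard error is 4/√100 = 0.4. True means of 3.0, 3.5 and 4.0% give noncentrality (5 − mean)/0.4 = 5.0, 3.75 and 2.5, and power 0.9996, 0.981 and 0.799. The plan states >0.99, 0.98 and 0.80, so the table reproduces.

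**3. Illustration for contrast sensitivity.** These inputs are assumptions, not figures from the documents: SD of within-eye change 0.15 to 0.25 log unit, equal in both eyes; shared loss S of 0.03 or 0.05; L = 0; 30 or 100 pairs. It is also assumed that the one-sided limit is a lower limit on loss, compared with zero. The chance that this limit exceeds zero is P(T > t), where T is noncentral t on n − 1 degrees of freedom with noncentrality S√n/SD, and t = 1.699 (n = 30) or 1.660 (n = 100).

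| SD | S | Noncentrality, n = 30 | Excludes zero, n = 30 | Noncentrality, n = 100 | Excludes zero, n = 100 |
|---|---|---|---|---|---|
| 0.15 | 0.03 | 1.10 | 28% | 2.00 | 63% |
| 0.15 | 0.05 | 1.83 | 56% | 3.33 | 95% |
| 0.20 | 0.03 | 0.82 | 20% | 1.50 | 44% |
| 0.20 | 0.05 | 1.37 | 38% | 2.50 | 80% |
| 0.25 | 0.03 | 0.66 | 16% | 1.20 | 33% |
| 0.25 | 0.05 | 1.10 | 28% | 2.00 | 63% |

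The paired difference in change has mean zero here, so its rate is 5% throughout.

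In the other direction, take a true L of 0.05 exactly offset by a shared gain of 0.05. The within-eye limit excludes zero in 5% of trials. With between-eye correlation of change from 0 to 0.5, the paired limit does so in 19-56% at 30 pairs and 41-95% at 100 pairs.

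**4. Precision cost.** The one-sided 95% half-width is t·SD/√n within eye and t·SD·√(2(1 − ρ))/√n paired, where ρ is the correlation between the two eyes' changes. At SD 0.20:

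| n | Within-eye | Paired, ρ = 0 | ρ = 0.3 | ρ = 0.5 | ρ = 0.7 |
|---|---|---|---|---|---|
| 30 | 0.062 | 0.088 | 0.073 | 0.062 | 0.048 |
| 100 | 0.033 | 0.047 | 0.039 | 0.033 | 0.026 |

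The paired interval is wider only when ρ is below 0.5.

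**The case against.** A reader might infer that the plan conceals shared change, so that a LAL loss could go unseen or be wrongly declared. The documents do not support that. The wording in 8.6 covers eyes in general, and 8.2 requires LAL and Control summaries separately, so the Control eyes' loss appears beside the LAL loss. Section 8.2 also requires a descriptive between-eye difference. If that is applied to the change, its mean, SD and n yield the missing limit directly.

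A reader might also take the percentages above as error rates of the trial. They are not. Contrast sensitivity has no hypothesis, margin or decision rule, and the safety parameter named in 5.2 is the incidence of ocular serious adverse events. Section 8.6 does not say which side the one-sided interval is on. If it is an upper limit on loss, as for cell loss, a shared change still moves it by the full amount S, but the frequencies in the table do not apply. The assumed shifts of 0.03 to 0.05 are a tenth to a sixth of the plan's eye-level threshold of 0.3 log unit and have no source in the documents. The substudy size is not given, so 100 pairs may be too many.

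Further, the two eyes hold different lens models, so not every postoperative change need be equal in both. Control eyes may have a secondary surgical intervention (SSI), for which 8.5.1 has a rule only for the effectiveness endpoints. Finally, 8.2 promises a detailed SAP before database lock, which could add this analysis.

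These points limit the severity. They do not supply an interval for the LAL-minus-Control contrast, and no section plans one.

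**Conclusion.** The point holds as a gap in analysis choice. Contrast sensitivity has an interval only for within-eye loss, which in LAL eyes estimates treatment effect plus shared change. The paired contrast that matches the stated safety comparison is described at most, without a limit, while cell loss in the same section has one.

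How much this matters cannot be determined from the documents. The illustrative 16-56% and 33-95% rest on the assumed SD, shared loss, numbers of pairs and lower-limit reading; with S = 0 the within-eye interval is unbiased. This is a worthwhile, inexpensive improvement to a supportive safety summary, not an error in a decision rule.

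**What to change.** In section 8.6, or in the detailed SAP, add for each spatial frequency and test condition, over subjects with both eyes tested:

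- the paired LAL-minus-Control difference in change from Week 3 to Month 6, which isolates the light-treatment period;
- the paired LAL-minus-Control difference at Month 6, which also captures a lens effect already present at Week 3.

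Give each a one-sided 95% t-based limit in the direction that bounds LAL loss (an upper limit when expressed as loss, as for endothelial cell loss). Keep the within-eye summaries as planned. State the substudy size and the side of the existing one-sided interval.

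State a rule for Control eyes with an SSI: either extend the pre-SSI rule of 8.5.1 or add a sensitivity analysis excluding those eyes. Contrast sensitivity is scheduled only at Week 3 and Month 6, so carrying a Week 3 value forward would set the Control change to zero. For the difference in change, the exclusion analysis is therefore the more informative of the two.

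The cost is SAP wording, a few more table columns, and a wider interval if the two eyes' changes correlate below 0.5. No visit or test is added to the schedule in Tables 2 and 3.

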8.7 SEQUENCE OF PLANNED ANALYSES

8.7.1 INTERIM ANALYSIS OF ECD

Based on RxSight's previous PMA, no significant ECD loss due to LAL light treatments was demonstrated. Therefore, the ECD loss is primarily due to the corneal trauma during cataract surgery. In order to evaluate the effect of LAL with the RxSight Insertion Device, an interim analysis on the ECD will be performed when all eyes have a chance to complete the Postop Week 3 examination.

All the analyses described in Section 8.6 will be performed based on the preoperative and Postop Week 3 ECD data. The interim analysis will also include the summaries of baseline characteristics and adverse events. No other study parameters will be summarized. No masking of the visual acuity will be broken and study will not be stopped due to the finding of the ECD outcomes. The purpose of this interim analysis is strictly administrative. Therefore, no p-value adjustment for the interim analysis will be performed.

8.7.2 FINAL ANALYSES

When all enrolled subjects have completed or exited the study, the final statistical analyses based on the SAP will be performed.

9 ADVERSE EVENTS

If an adverse event (AE) occurs, the first concern will be the safety and welfare of the subject; treatment should be provided as appropriate for the event. During the study, the Investigator should appropriately treat and follow each AE until it resolves, stabilizes, or it is determined that further improvement is not expected.

9.1 ADVERSE EVENT DEFINITIONS

An adverse event (AE) is any untoward medical occurrence, unintended disease or injury, or untoward clinical signs (including abnormal laboratory findings) in subjects, users, or other persons, whether or not related to the investigational medical device.

Note 1 to entry: This definition includes events related to the investigational medical device or the comparator.

Note 2 to entry: This definition includes events related to the procedures involved.

Note 3 to entry: For users or other persons, this definition is restricted to events related to investigational medical devices.

Unanticipated Adverse Device Effects (UADE) are any serious adverse effect on health or safety or any life-threatening problem or death caused by, or associated with a device, if that effect, problem, or death was not previously identified in nature, severity or degree of incidence in the investigational plan or application (including a supplementary plan or application), or any other unanticipated serious problem associated with a device that relates to the rights, safety, or welfare of subjects.

An investigator will submit to the Sponsor and to the reviewing IRB a report of any UADE occurring during an investigation as soon as possible, but in no event later than 10 working days after the investigator first learns of the effect. The Sponsor will immediately conduct an evaluation of any unanticipated adverse device effect. The results of the evaluation will be reported to FDA and to all reviewing IRB's and participating investigators within 10 working days of the Sponsor becoming aware of the event. Thereafter the Sponsor shall submit additional reports concerning the effect as FDA requests. If a UADE is determined by the Sponsor to present an unreasonable risk to study subjects, all investigations or parts of the investigation presenting that risk will be terminated as soon as possible. Termination will occur not later than 5 working days after this determination is made, and not later than 15 working days after first receiving notice of the event. The investigation will not be resumed without IRB and FDA approval.

The following need to be reported as AEs as specified:

[figure not shown]
1. Anterior Chamber Inflammation

• Iritis/cells/flare (if present after Postop Week 1 and greater than grade 1 (trace)) or (any iritis/cells/flare present at Postop Month 6 of any grade) OR

• Chronic anterior uveitis (Persistent anterior segment inflammation characterized by grade 1+ cell or greater using Standardization of Uveitis Nomenclature criteria; persistent for greater than 3 months after surgery, or relapses in less than 3 months after discontinuation of therapy, or the subject is maintained on therapy for more than 3 months to control inflammation).

[figure not shown]
2. Corneal edema:

- If present after Postop Week 1 and greater than grade 1 (trace)) or (if present at Postop Month 6 of any grade) OR
- Corneal swelling (stromal or epithelial) resulting in BCDVA ≤20/40 after Postop Week 3)
- 3. Raised intraocular pressure (IOP) >10 mmHg above preoperative and greater than 25 mmHg (if present after Postop Week 1) AND unrelated to mechanical pupillary block

Adverse Event	Definition
Clinically significant cystoid macular edema	Macular edema diagnosed by clinical examination and adjunct testing (e.g., OCT, FA, or other method) resulting in reduced BCDVA to20/40 or worse after Postop Week 3
Endophthalmitis	Postoperative intraocular inflammation requiring vitreous tap and use of intraocular antibiotics
Mechanical pupillary block	A shallowing of the peripheral and/or central anterior chamber with or without elevation of IOP by obstruction of the flow of aqueous humor from the posterior chamber through the pupil to the anterior chamber. This may be induced by the crystalline lens, vitreous face, or implanted devices
Rhegmatogenous Retinal Detachment	Partial or complete retinal detachment associated with retinal tear
Toxic anterior segment syndrome	An acute, noninfectious inflammation of the anterior segment of the eye that develops within 24 to 48 hours after surgery and is characterized by corneal edema and accumulation of white cells in the anterior chamber of the eye
Secondary IOL intervention	Exchange: The investigational device is replaced with the same lens model. Removal: The investigational device is removed and replaced with a noninvestigational lens or no lens is implanted.
	Reposition: The existing IOL is surgically moved to another location or rotated.

In addition, the following definition should be used when considering retinal toxicity as an adverse event:

All adverse events should be reported and information provided regarding whether the adverse event meets the above definitions.

9.2 SERIOUS ADVERSE EVENT DEFINITION

Serious Adverse Events (SAEs) are AEs that lead to:

- death
- a serious deterioration in the health of the subject that:
 - results in a life-threatening illness or injury
 - results in a permanent impairment of a body structure or function (e.g., blindness)
 - requires in-subject hospitalization or prolongation of existing hospitalization
 - results in medical or surgical intervention to prevent permanent impairment to a body structure or a body function
- fetal distress, fetal death, or a congenital abnormality or birth defect
- a potentially sight-threatening condition
- or is another important medical event.

9.2.1 IDENTIFICATION AND COLLECTION

Identification and collection of an AE begins after informed consent has been obtained and documented. Standard sources of identifying AEs include:

• direct observation by the Investigator or study team member

- asking the study participant a specific question (e.g., "Since your last visit, have you experienced any problems with your eyes or vision?")
- unsolicited volunteering of information by the study participant (e.g., "Doctor, I have had numerous headaches since I started using this lens.")

Ocular AEs and SAEs and systemic SAEs observed or elicited by the Investigator, reported by the subject, or resulting from a test result, etc., occurring during the clinical investigation must be documented. During the study, the Investigator should treat the study subject as appropriate to ensure his/her safety and welfare. Refer to Section 7.7.1 for additional information pertaining to ongoing AEs at subject exit.

Pre-existing conditions will not be considered AE/SAEs but will be collected at the Preoperative Visit as medical history. A worsening of a pre-existing condition during the study should be documented as an AE and evaluated accordingly.

Hospitalization is a criterion for assessment of seriousness. Hospitalization in the absence of a medical AE is not in itself an AE. For example, the following reports of hospitalization without a medical AE should not be considered either an SAE or an AE:

- Planned hospitalization for a pre-existing condition without serious deterioration in health (e.g., planned knee replacement surgery)
- Social admission (e.g., subject has no place to sleep)
- Administrative admission (e.g., for yearly physical exam or elective procedures not related to the study)
- Optional admission not associated with a precipitation medical AE (e.g., for elective cosmetic surgery)

9.2.2 EVALUATIONS

When evaluating AEs, the Investigator must determine if the event is serious, assess the severity of symptoms, the relationship of the event to the device or study protocol, using the following guidelines:

1. Severity

Mild: subject awareness of a sign or symptom that is easily tolerated, requires no treatment, and does not interfere with subject's daily activities

Moderate: subject awareness of a sign or symptom which may be a low level of concern to the subject and may interfere with daily activities, but can be relieved by simple therapeutic care

Severe: a sign or symptom that interrupts the subject's daily activity and requires systemic therapy or other treatment

2. Relationship (Causality) to Study Device or Study Protocol

Related: There is at least a reasonable possibility that the AE/SAE is related to the study device or study protocol. Reasonable possibility means that there is evidence to suggest a causal relationship between the study device or study protocol and the AE. **Unrelated:** There is little or no reasonable possibility that the AE/SAE is related to

the study device or study protocol. This assessment implies that the AE/SAE has little or no temporal relationship to the study device and/or a more likely or certain alternative etiology exists.

